4.3 JUSTIFICATION FOR DOSE

Pyronaridine will be administered as a single oral dose on Day 8, with different doses to be tested across and within cohorts in order to effectively characterise the PK/PD relationship. Each cohort will comprise up to three dose groups, with participants randomised to a dose group on the day of dosing. For each cohort, the SDRT will meet between Day 0 and Day 8, to decide on the dose/s to be administered. Dose selection will be decided based on number of participants inoculated with the malaria challenge agent, and when applicable available data from previous cohorts.

The highest dose of pyronaridine administered will be no more than 720 mg. This dose is equal to the maximum single daily dose of pyronaridine administered to adult patients ≥ 65 kg treated with Pyramax® (pyronaridine/artesunate combination) in accordance with manufacturer's product information for the treatment of acute uncomplicated malaria. Pyramax® is administered as a multiple dose treatment course (daily dosing with 720 mg pyronaridine/ 240 mg artesunate over three days for adults ≥ 65 kg), thus the total exposure to pyronaridine following administration of a single dose of 720 mg in the current study is expected to be lower than occurs during a course of Pyramax® treatment. A dose of 720 mg may be required to determine the maximum killing rate (E_{max}) of pyronaridine in the IBSM model.

The lowest dose of pyronaridine administered in this study will be no less than 180 mg. Modelling studies using clinical PK data and preclinical PD data (*in vitro* and murine studies) have indicated that a dose as low as 180 mg may be required for parasite regrowth to occur following initial parasite clearance. Parasite regrowth is required in this study to calculate all PK/PD parameters (primary endpoint).

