3. PROJECT OVERVIEW

3.1 Study Design

This was a single-centre, open-label phase 1b study using the *P. falciparum* induced blood stage malaria (IBSM) model to characterise the PK/PD profile of pyronaridine.

Up to 18 healthy, malaria naïve adult participants are planned to be enrolled into this study, in cohorts of up to six participants each. Following a screening period of up to 28 days, cohorts of up to 6 healthy participants will be enrolled. After confirmation of eligibility, including a Rapid Antigen Test (RAT) for SARS-CoV-2, each participant will be inoculated intravenously on Day 0 with approximately 2,800 viable *P. falciparum*-infected erythrocytes. Participants will be followed up daily via phone call or text message on Days 1 to 3 post-inoculation to solicit any adverse events.

Participants will attend the clinical unit once on Days 4, 5, 6 and 7 for clinical evaluation and blood sampling to monitor the progression of parasitaemia, using quantitative polymerase chain reaction (qPCR) targeting the gene encoding 18S rRNA (referred to hereafter as malaria 18S qPCR).

Participants will have a nasopharyngeal aspirate (NPA) for SAR-CoV-2 on Day 6 am, and blood collected on Day 7 am to monitor haematology and biochemistry.

Participants will be admitted to the clinical trial unit on Day 8 for dosing with the investigational medicinal product (IMP; pyronaridine) when parasitaemia for the majority of participants is expected to be above 5,000 parasites/mL. Participants will need to have a negative SARS-CoV-2 RAT prior to admission.

Pyronaridine will be administered as a single oral dose. Different doses of pyronaridine will be administered across and within cohorts in order to effectively characterise the PK/PD relationship. Each cohort will comprise up to three dose groups, with participants randomised to a dose group on the day of dosing. The highest dose of pyronaridine administered will be no more than 720 mg; the lowest dose administered will be no less than 180 mg.

The proposed dosing regimen for the Cohort 1 assuming six participants are enrolled, is as below. If less than six Participants are enrolled the Safety Data Review Team (SDRT) will meet between Day 0 and Day 8, to decide on the dose/s to be administered.

	Dose group		
	1A (n=2)	1B (n=2)	1C (n=2)
Pyronaridine	360 mg	540 mg	720 mg

The SDRT will review safety, tolerability, parasitaemia and PK/PD data to determine the dose to be administered to Cohort 2.

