4. STATISTICAL CONSIDERATIONS

Data analysis will be performed according to the Sponsor's representative Standard Operating Procedures (SOPs).

The general analytical approach for all endpoints will be descriptive in nature. All summaries will present the data by dose group as well as by all participants combined.

Unless otherwise stated, the following statistical approaches will be taken:

Continuous variables:	Descriptive statistics will include the number of non-missing values, mean, standard deviation (SD), CV%, median, interquartile range, minimum, and maximum. The minimum and maximum values will be presented to the same number of decimal places as recorded in the raw data; mean and median will be presented to 1 decimal place more than raw data; and SD will be presented to two more decimal places than the raw data. The number of decimals for lab parameters may be reduced if the full presentation of the data includes more than 4 significant figures. In general, the mean and median will be reported with one decimal place more than the data, and the standard deviation will be reported with two decimal places more than the data.
Categorical variables:	Descriptive statistics will include frequency counts and percentages per category. Percentages will be rounded to one decimal place, with the denominator being the number of patients in the relevant population.
Imputation:	No imputation will be performed for missing data.
Confidence intervals (CIs):	CIs will be two-sided and will use 95% confidence levels. Any analyses requiring significance testing will use a two-sided test at the 5% significance level.
Unscheduled Visits	Unscheduled visits that do not have laboratory data on the same visit date will be excluded from summary tables.
Early termination visit	Assessments conducted at Early Termination will be excluded from visit-based summary tables.

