4.2.1.2 PD Analysis

Data manipulation and data analyses for all PD data will be performed using R (highest version available).

4.2.1.3 *PK Analysis*

The estimation of pharmacokinetic parameters by non-compartmental analysis (NCA) methods will be performed using Phoenix WinNonlin software (v8.3 or a more recent version, Certara USA, Inc., USA).

4.2.1.4 *PKPD Analysis*

All data processing, analysis, model setup and modeling result analysis including goodness-of-fit plots will be performed in R 4.1.3 and IQRtool package 1.10.0 [IQRtools]. NLME modelling will be performed with Monolix 2019R1 [MLX19] using Stochastic Approximation Expectation Maximization (SAEM) for parameter estimation.

4.2.2 *Baseline*

Baseline will be defined as:

Safety

- The last scheduled observation prior to the administration of the malaria challenge inoculum [Inoculation Baseline],
- The last scheduled observation prior to the first administration of IMP [Treatment Baseline].

PD

- The last observation prior to the administration of the IMP for PD data.

PK

- The last observation prior to the administration of the IMP for PK data.

4.2.3 *Change from Baseline*

Change from Baseline will be calculated as:

$$\text{Change from baseline} = (\text{postbaseline value}) - \text{baseline value}$$

4.2.3.1 *Days relative to Inoculation*

$$\text{Days} = (\text{Assessment Date} - \text{Inoculation Administration Date}) + 1$$

4.2.3.2 *Days relative to IMP administration*

$$\text{Days} = (\text{Assessment Date} - \text{First Study Drug Administration Date}) + 1$$

4.2.4 *IMP Treatment Groups*

Tabulations will summarise data by the following IMP groups and these may vary for each cohort:

Pyr 360 mg
Pyr 540 mg
Pyr 720 mg
Overall

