$$95\% \text{ CI: } 10^{-48(\beta_{1,i} \pm 1.96 \times SE(\beta_{1,i}))} \quad (3)$$

where $\beta_{1,i}$ and $SE_{\beta(1,i)}$ are the slope and corresponding standard error of the slope parameter of the optimal linear regression model, respectively.

Estimating Dose Specific PRR (PRR_{48,D})

Of the s participants with appropriate overall fit ($p < 0.001$), the average PRR_{48} and corresponding 95% CI for each cohort is estimated by using the inverse variance method to calculate the weighted average linear regression slope ($\bar{\beta}_1$) and corresponding SE. The weighted average slope for s participants in the dose with appropriate overall fit is given by Equation (4):

$$\bar{\beta}_1 = \frac{\sum_{i=1}^s (w_i \times \beta_{1,i})}{\sum_{i=1}^s w_i}, \quad i = 1, \dots, s \quad (4)$$

where the weight is the inverse of the squared standard error, $w_l = \frac{1}{SE(\beta_{1,l})^2}$. The standard error of $\bar{\beta}_1$ is estimated as, $SE(\bar{\beta}_1) = \sqrt{\frac{1}{\sum_{l=1}^s w_l}}$.

Therefore the dose specific PRR (PRR_{48,D}) and corresponding 95% confidence interval is estimated as shown in Equation (5) and (6), respectively:

$$PRR_{48,D} = 10^{-48 \times \bar{\beta}_1} \quad (5)$$

$$95\% CI: 10^{-48 \times (\bar{\beta}_1 \pm 1.96 \times SE(\bar{\beta}_1))} \quad (6)$$

Parasite Clearance Half Life

The parasite clearance half-life (PCt_{1/2}) will be derived from the optimal decay rate. The relationship between PRR₄₈ and parasite clearance half-life (PCt_{1/2}) is a simple transformation of the PRR₄₈ as shown in Equation (7):

$$PCt_{1/2} = \log_{10}(2) \times \left(\frac{48 \text{ hours}}{\log_{10}(PRR_{48,l})} \right) = \frac{\log_{10}(2)}{-\beta_{1,l}} \quad (7)$$

where PRR_{48,i} is the parasitaemia ratio estimated over a 48-hour interval that is subsequently transformed into a per hour clearance rate.

Comparison of Dose Specific PRR₄₈

To determine whether there are differences between dose specific PRRs, an omnibus test for between group differences is used. The test is used to assess whether there are differences in the weighted mean slope of the J doses, using the test statistic shown in Equation (8),

$$Q_B = \sum_{j=1}^J w_{j.} (\bar{\beta}_{j.} - \bar{\beta}_{..})^2 \sim \chi_{J-1}^2 \quad j = 1, \dots, J \quad (8)$$

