The weight for the j^{th} dose is denoted by $w_{j.} = \sum_{i=1}^{s_j} w_{ij}$ for participant i with appropriate overall fit in dose j . The $\bar{\beta}_{j.}$ is the weighted average slope for dose j as defined in Equation (9), and $\bar{\beta}_{..}$ is the weighted grand mean given by:

$$\bar{\beta}_{..} = \frac{\sum_{j=1}^J w_{j.} \bar{\beta}_{j.}}{\sum_{j=1}^J w_{j.}} \quad (9)$$

Post-hoc pair-wise comparisons can be calculated using the test statistic $Z_G = \frac{G}{\sqrt{v_G}}$, where G is the contrast ($G = c_1 \bar{\beta}_1 + \dots + c_J \bar{\beta}_J$) and v_G is the variance of the contrast ($v_G = \frac{c_1^2}{w_{1.}} + \dots + \frac{c_J^2}{w_{J.}}$). The p-value of the L pair-wise comparisons can be calculated using the Scheffe method, by comparing Z_G^2 to a chi-squared distribution with $L - 1$ degrees of freedom.

Parasite Regrowth

Incidence of parasite regrowth will be reported as the number and percentage of participants in each dose group, with regrowth defined as ≥ 5000 parasites/mL and a two-fold parasitaemia increase within 48 hours after initial reduction in parasitaemia.

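### SAP 11.1.2 refers the Scheffé pairwise statistic to chi-squared on L − 1 degrees of freedom (L = number of comparisons); it should be J − 1 (J = number of doses), and the two agree only when L = J.

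*SAP*

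**What the plan says.** SAP 11.1.2, under the comparison of dose-specific PRR48, has two steps.

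- **Omnibus step, Equation (8).** Q_B assesses whether "there are differences in the weighted mean slope of the J doses" and is referred to chi-squared on J − 1 degrees of freedom.
- **Post-hoc step.** Each pair is a contrast G with variance v_G, and Z_G = G/√v_G. The p-values of the L "pair-wise comparisons can be calculated using the Scheffe method, by comparing" Z_G² "to a chi-squared distribution with $L - 1$ degrees of freedom".

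The SAP does not say whether all pairs or only some will be tested. On level and sidedness, SAP 4 says: "Any analyses requiring significance testing will use a two-sided test at the 5% significance level".

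The number of doses is not fixed. SAP 4.2.4 lists 360, 540 and 720 mg but introduces them with "Tabulations will summarise data by the following IMP groups and these may vary for each cohort". SAP 3.1 says: "Each cohort will comprise up to three dose groups, with participants randomised to a dose group on the day of dosing". Protocol 4.3 sets the floor: "The lowest dose of pyronaridine administered in this study will be no less than 180 mg". The same section says that modelling pointed to a dose that low as possibly needed to see regrowth.

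**The concern.** Scheffé's bound protects every contrast among J group means at once. Its degrees of freedom depend on how many means there are, not on how many contrasts someone chooses to look at. A rule that counts comparisons breaks the link between the omnibus test and the pairwise tests that follow it.

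The three listed doses hide the error, because three doses happen to have three pairs. If the analysed set of doses or pairs differs, a programmer who follows the text literally will report wrong pairwise p-values. They are too large when there are more comparisons than doses and too small when there are fewer.

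**Working it through.** **Inputs**

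- J = number of doses; omnibus reference chi-squared on J − 1 (SAP 11.1.2, Equation (8)).
- L = number of pairwise comparisons; post-hoc reference chi-squared on L − 1 (SAP 11.1.2).
- Level 5%, two-sided (SAP 4).
- Listed doses: three (SAP 4.2.4). Tablets are 180 mg and the limits are given as one and four tablets (Protocol 6.1.2 and 6.2.2), so whole tablets allow four doses: 180, 360, 540 and 720 mg.

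**Step 1. The correct degrees of freedom.** Let b_j be the weighted mean slope for dose j, w_j its weight and b.. the weighted grand mean. For a contrast with Σc_j = 0, G = Σc_j b_j = Σc_j(b_j − b..). By the Cauchy–Schwarz inequality,

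G² ≤ (Σ c_j²/w_j) · (Σ w_j(b_j − b..)²) = v_G · Q_B,

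so Z_G² = G²/v_G ≤ Q_B. Equality holds at c_j proportional to w_j(b_j − b..). The largest Z_G² over all contrasts is therefore Q_B, which Equation (8) places on J − 1. A simulation with 200,000 null draws for each J from 2 to 6 and for J = 9, with arbitrary weights, matched this identity to about 1e-14.

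**Step 2. When the SAP rule agrees.** L − 1 = J − 1 only if L = J. If all pairs are tested, L = J(J − 1)/2, and J(J − 1)/2 = J gives J = 3.

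**Step 3. The listed case.** With J = 3 and all pairs, L = 3. Both rules give 2 degrees of freedom, a critical value of 5.991 and an error over all contrasts of 0.0500. The SAP rule is right here.

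**Step 4. Four doses, all pairs.** L = 4 × 3/2 = 6.

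| | SAP rule | Scheffé |
|---|---|---|
| Degrees of freedom | 5 | 3 |
| 5% critical value of Z_G² | 11.070 | 7.815 |
| Same, as \|Z\| | 3.327 | 2.795 |
| Familywise error, all contrasts | 0.0114 | 0.0500 |
| Familywise error, pairs only (simulated, one arbitrary weight set) | 0.0046 | 0.0261 |
| p at Z = 3.0 (Z² = 9.0) | 0.109 | 0.029 |

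Any pair with |Z| between 2.795 and 3.327 changes from significant to not significant.

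**Step 5. Fewer pairs than doses.** With J = 3 and L = 2, the SAP rule uses 1 degree of freedom and a critical value of 3.841. On the correct 2 degrees of freedom, P(χ² > 3.841) = exp(−3.841/2) = 0.147. This is the error over all contrasts. For the two tested pairs alone it cannot exceed 2 × 0.05 = 0.10. With J = 4 the error over all contrasts is 0.279 for L = 2, 0.112 for L = 3, 0.050 for L = 4 (agreement) and 0.023 for L = 5.

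**Step 6. Two doses.** L = 1 and the post-hoc step has 0 degrees of freedom, so it gives no usable test. There is then only one contrast, Z_G² equals Q_B, and Equation (8) already tests it on 1 degree of freedom with critical value 3.841.

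**The case against.** The strongest defence is that little depends on these tests. The SAP says they can be calculated, not that they will be. They are post hoc, on a secondary endpoint, in a study whose general approach SAP 4 calls descriptive. The result lists in SAP 11.1.3 and Appendix Table A name no pairwise output. Q_B, the dose-specific PRR48 values and their confidence intervals do not use the faulty reference distribution, and no dose-selection or stopping rule is tied to these p-values. For the three listed doses with all pairs tested, the answer is correct. In the four-dose, all-pairs case the error is conservative, so it can hide a dose difference but not create one. All of this stands, and it limits the size of the point. It does not make the formula valid.

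A reader might infer more than the documents support, in three ways.

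- *The rule is wrong unless exactly three doses are compared.* This holds only if all pairs are tested, which the SAP does not state. Four of the six pairs at J = 4 give the right degrees of freedom, and two of the three pairs at J = 3 do not.
- *With two doses there is no p-value.* That is true only of a redundant second step; Q_B supplies the valid test.
- *With five or more doses the error is far larger.* The arithmetic is true, but whole 180 mg tablets between the stated limits allow only four doses. Protocol 6.2.2 calls the tablets scored, so a split tablet is not physically excluded, but no section plans one.

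L might also have been meant as the number of doses. The sentence attaches L to the comparisons and J already denotes doses, so the text would need the same correction.

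**Conclusion.** The point holds as a minor formula error. The degrees of freedom should be J − 1, and the written rule is correct only when the number of comparisons equals the number of doses.

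The realistic failing case is the addition of a 180 mg group with all six pairs tested, where p at Z = 3.0 is 0.109 instead of 0.029. Testing fewer pairs than doses errs the other way. J can also fall below the number of doses given, because only participants whose regression has p < 0.001 contribute and Cohort 1 plans two participants per dose.

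The figures treat the inverse-variance weights as known, as Equation (8) does. The four-dose figures also assume that 180 mg is added to the three listed doses; the documents allow this but do not commit to it. The consequence is confined to optional pairwise p-values and does not reach the primary PK/PD analysis.

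**What to change.** In SAP 11.1.2, replace L − 1 with J − 1 in the sentence on the Scheffé method, and define J there and in Equation (8) as the number of doses with at least one participant whose log-linear fit is appropriate. State which pairs will be compared. Add that with J = 2 the post-hoc step is omitted because Q_B already is that comparison.

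The cost is one symbol and a sentence or two in the SAP, and the matching argument in the R code. No new data are needed, and nothing changes if all pairs of three doses are compared. If the SAP is not reissued, the correction can be recorded in the clinical study report, where SAP 2 already places significant changes from the planned analyses.

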8.1.6 OUTPATIENT MONITORING POST-IMP ADMINISTRATION (DAY 13 TO DAY 50±2)

Follow up visits will be undertaken on an out-patient basis for clinical evaluation and blood sampling. Follow up visits will occur at least three times per week (may occur more frequently if clinically indicated) until Riamet® treatment.

The following procedures will take place during these visits:

- Obtain 12-lead ECG.
- Record vital signs.
- Record AEs and use of concomitant medications.
- Check participant diary cards.
- Perform symptom-directed physical examination if clinically indicated.
- Collect blood samples for drug concentration at 120 (Day 13±1), 168 (Day 15±1), 216 (Day 17±1), 288 (Day 20±1), 336 (Day 22±1), 384 (Day 24±1), 456 (Day 27±1), 504 (Day 29±1), 576 (Day 32±2), 744 (Day 39±2) and 864 (Day 44±2) hours (Days) post-dose
- Collect blood samples for malaria 18S qPCR at least 3 times per week until Riamet® treatment, timing will be at PI discretion based on previous 18S qPCR results and clinical symptoms. Where possible 18S qPCR blood sampling should coincide with drug concentration sampling time-points to avoid bringing participants back for outpatient visits unnecessarily.
- Collect blood samples for haematology and biochemistry on Days 15±1, 22±1, 29±1, 37±2 and 44±2.
- Collect blood samples for parasite lifecycle stage qRT-PCR at Investigator's discretion (if gametocytæmia is suspected based on low and stable parasitaemia). These samples should be aligned with the 18S qPCR to avoid bringing participants back for outpatient visits unnecessarily.
- Collect blood samples for malaria future research (if participant has consented) on Days 15±1 and 29±1.

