8.1.7 ANTIMALARIAL RESCUE TREATMENTS

All participants will receive compulsory antimalarial rescue treatment with Riamet® on Day 47±2, or earlier in the following cases:

- Parasitaemia is not reduced by approximately 10-fold at the end of the 96 hour confinement period (Day 12) when compared with peak parasitaemia.
- Parasite regrowth occurs after an initial reduction in parasitaemia, with regrowth defined as ≥ 5000 parasites/mL and a 2-fold parasitaemia increase within 48 hours.
- Volunteer discontinuation/withdrawal from the study (see Section 7.2).
- Investigator's discretion in the interest of participant safety.

As qPCR results are not received in real-time, rescue may occur when these parasitaemia thresholds are presumed to have occurred.

If gametocytes are present as determined by qRT-PCR at any time point after the confinement period, a single dose of Primacin® will be administered at the Investigator's discretion. A participant's G6PD status will determine the dose of primaquine administered. If an allergy or contraindication to Riamet® or Primacin® develops, Malarone® will be administered. In the rare event that a participant cannot tolerate oral drugs, participants will be admitted to hospital and I.V. artesunate will be administered.

The following procedures will be performed prior to antimalarial rescue treatment:

- Perform symptom-directed physical examination if clinically indicated.
- Obtain a 12-lead ECG.
- Record vital signs.
- Record AEs and use of concomitant medications.
- Check participant diary cards.
- Collect blood samples for
 - haematology and biochemistry,
 - malaria 18S qPCR,
 - drug concentration
- Collect sample for parasite viability *ex vivo* growth. **NOTE only if antimalarial rescue treatment is administered prior to Day 47±2.**

Please note if a participant receives antimalarial rescue treatment after administration of pyronaridine but prior to Day 47±2, drug concentration, haematology, biochemistry and future malaria research blood collection will still be required for the full duration of the trial. Following antimalarial rescue treatment blood will be taken for 18S qPCR at the completion of Riamet and until at least one negative result is obtained.

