8.2.2 PHARMACODYNAMICS

Malaria 18S qPCR

Blood will be collected to quantify total malaria parasitaemia by quantitative polymerase chain reaction targeting the gene encoding *P. falciparum* 18S rRNA (malaria 18S qPCR; reported as parasites/500uL packed RBCs). Malaria 18S qPCR data will be used to calculate the PK/PD parameters of pyronaridine (the primary endpoint) and to determine the kinetics of parasite clearance following pyronaridine dosing (secondary endpoint). Malaria 18S qPCR will also be used to monitor the parasitaemia of participants in real time in order to guide the timing of antimalarial rescue treatment initiation.

Samples for malaria 18S qPCR will be analysed using a validated analytical method in compliance with the SOPs of the laboratory performing the analyses. Assays will be performed in a Sponsor approved laboratory.

Blood for malaria 18S qPCR will be collected on Day 0 prior to inoculation with the malaria challenge agent, then once daily on Days 4, 5, 6 and 7. On Day 8, blood will be collected pre-pyronaridine administration, then at the following hours post-pyronaridine administration while confined in the clinical unit: 4, 8, 12, 16, 20, 24, 30, 36, 42, 48, 60, 72, 84 and 96 hours.

As outpatients, participants will have blood collected at least three times per week until antimalarial rescue treatment. Timing will be at PI discretion based on previous malaria 18S qPCR results and clinical symptoms. Where possible, malaria 18S qPCR blood sampling should coincide with drug concentration sampling time-points to avoid unnecessary outpatient visits. Following antimalarial rescue treatment, no further blood collection for malaria 18S qPCR is required for a participant once a minimum of two negative results are recorded.

Allowed time windows for sample collection are specified in Section 8.4.

Parasite lifecycle stage_qRT-PCR

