8.4 ALLOWED TIME WINDOWS

The following time windows will be allowed for vital signs recording, ECGs and blood sampling for clinical laboratory evaluations:

Time point	Allowed time window
Malaria inoculation (Day 0)	± 4 hours
Outpatient monitoring pre-IMP (Days 4-7)	± 12 hours
Inpatient observation pre-IMP (Day 8)	± 2 hours
Inpatient observation ≤24 hours post-IMP (Day 8-9)	± 30 minutes
Inpatient observation >24 hours post-IMP until discharge (Day 9-12)	± 60 minutes
Outpatient monitoring from discharge up to and including Day 30	± 24 hours
Outpatient monitoring from Day 31 until EOS visit	± 2 days

The following time windows will be allowed for blood sampling to quantify pyronaridine blood concentrations and to monitor malaria parasitaemia:

Time point	Allowed time window
Malaria inoculation (Day 0)	± 4 hours
Outpatient monitoring pre-IMP (Days 4-7)	± 12 hours
Inpatient observation pre-IMP (Day 8)	± 60 minutes
Inpatient observation ≤24 hours post-IMP (Day 8-9)	± 30 minutes
Inpatient observation >24 hours post-IMP until discharge (Day 9-12)	± 60 minutes
Outpatient monitoring from discharge up to and including Day 30	± 24 hours
Outpatient monitoring from Day 31 until EOS visit	± 2 days

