9.4.3 ANALYSIS OF THE SECONDARY ENDPOINTS

This study has three secondary endpoints.

Safety parameters:

The safety and tolerability of pyronaridine will be assessed by clinical review of the following parameters:

- AEs (including SAEs and AESIs)
- Vital signs
- 12-lead ECG
- Haematology, Biochemistry, urinalysis
- Physical examination

The analysis of this endpoint is discussed in Section 9.4.4 below.

Parasite clearance kinetics:

The parasite clearance kinetics following dosing with of pyronaridine will be determined by calculating the parasite reduction ratio over a 48 hour period (PRR₄₈) and corresponding parasite clearance half-life (PCt_{1/2}); the incidence of parasite regrowth (n and % per dose group) will be recorded.

The PRR₄₈ will be estimated using the slope of the optimal fit of the log-linear relationship of the parasitaemia decay. The optimal fit will be derived using summarised replicate parasitaemia data, which have been cleaned by dealing with potential outliers, values below the limit of detection and non-detectable values (ND). The optimal fit of the log-linear parasitaemia-by-time relationship is determined by using left and right censoring to systematically remove the potential lag phase and tail phase of the parasitaemia decay. The decay rate, estimated by the slope coefficient from the log-linear decay regression, will be calculated for each participant. The overall dose-specific PRR₄₈ will be estimated with its 95% CI by calculating the weighted average slope estimate and corresponding standard error (SE) using an inverse-variance method. Only participants who have optimal regression models with appropriate fit contribute toward the dose-specific PRR₄₈. Details will be presented in the SAP.

The parasite clearance half-life (Pt ½) will be derived from the optimal decay rate. PCt_{1/2} is a transformation of PRR₄₈ into a per hour clearance rate. Details regarding the calculation of this parameter will be presented in the SAP.

PK parameters:

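### Participants rescued for presumed regrowth can be reported as having none, because SAP 11.1.2 counts only a measured threshold and rescue ends observation

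*SAP*

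**What the plan says.** Protocol 9.4.3 announces the result: "the incidence of parasite regrowth (n and % per dose group) will be recorded". The definition is in SAP 11.1.2, under Parasite Regrowth: "Incidence of parasite regrowth will be reported as the number and percentage of participants in each dose group, with regrowth defined as" at least 5000 parasites/mL and a doubling within 48 hours, after an initial reduction.

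Protocol 8.1.7 uses the same rule as one of the triggers for early Riamet, "with regrowth defined as ≥ 5000 parasites/mL and a 2-fold parasitaemia increase within 48 hours", and then adds: "As qPCR results are not received in real-time, rescue may occur when these parasitaemia thresholds are presumed to have occurred". Protocol 8.2.2 says something different: "Malaria 18S qPCR will also be used to monitor the parasitaemia of participants in real time", in order to guide when rescue starts.

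On sampling, Protocol 8.1.6 says: "Collect blood samples for malaria 18S qPCR at least 3 times per week until Riamet® treatment". The exact timing is left to the PI in the light of earlier results and symptoms. Protocol 8.4 gives a window of ±24 h for the row "Outpatient monitoring from discharge up to and including Day 30" and ±2 days after that. Protocol 8.1.7 also has a list beginning "The following procedures will be performed prior to antimalarial rescue treatment", which includes an 18S qPCR sample.

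The SAP imputes nothing (section 4). Its disposition listing (section 7) gives the date of rescue medication but no reason. It has no rule for a participant rescued on presumption, and none for judging a 48-hour doubling when samples are further apart.

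**The concern.** The endpoint and the rescue trigger share one numeric rule, but rescue may come before the rule is seen to be met. Once Riamet is given, natural growth stops and the threshold can no longer be observed. A participant treated because parasitaemia was rising, whose last sample reads below 5000 parasites/mL, does not satisfy the definition. With no other category available, that person falls into the no-regrowth count. The accurate status is unknown.

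A second, weaker route is the 48-hour clause. If it is read as requiring two samples at most 48 h apart, a rise first seen across a longer gap does not qualify, however steep it is.

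A third concerns the denominator. Someone dosed with pyronaridine and then treated early for another reason stays in the dose group as a non-event, although follow-up for regrowth was cut short. Such reasons include investigator discretion, withdrawal, failure of the Day 12 reduction criterion, or SARS-CoV-2.

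Each route lowers the reported incidence. Protocol 4.3 suggests regrowth may need doses as low as 180 mg, so the low-dose groups are where this matters most.

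**Working it through.** There is no power or precision figure for regrowth incidence to reproduce, and the maximum of 18 has no formal basis (SAP 3.6). The check is arithmetic on the schedule and the definition.

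**1. Presumed rescue below the threshold.** Take, for illustration only, a pre-rescue value of 3,000 parasites/mL. The time to 5,000 is 48 × ln(5000/3000)/ln(G), where G is the fold growth per 48 h.
- For drug-free growth, 2,800 parasites on Day 0 and 5,000/mL on Day 8 (192 h), with an assumed blood volume of 5 L, give 2,800/5,000 = 0.56/mL. The rise is 5,000/0.56 = 8,929-fold, so G = 8,929^(1/4) = 9.7 (4 L: 9.2; 6 L: 10.2).
- At G = 9.7 the time is 48 × 0.511/2.272 = 10.8 h.
- At G = 2 it is 48 × 0.511/0.693 = 35.4 h.
- If residual drug stops the rise, 5,000 is never reached.

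The same measured value fits all three, so neither regrowth nor no regrowth is established.

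**2. Sampling gaps.**
- At three samples per week the mean gap is 168/3 = 56 h. On whole days at least one gap per week is 72 h; a 48/48/72 h week spends 72/168 = 43% of its time in that gap.
- Protocol 8.1.6 asks that qPCR coincide with drug-concentration visits where possible. From Day 12 to Day 47, 6 of the 12 gaps between those visits exceed 48 h (for example Days 17–20, 24–27 and 29–32), so further qPCR visits must fill in.
- With ±24 h windows a nominal 48 h gap can run from 0 to 96 h.

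**3. What the 48-hour clause does across a gap.** A simulation used 20,000 runs per setting, a 48/48/72 h week, and an assumed 5- to 30-fold growth per 48 h. It asked whether the first sample at or above 5000 meets the definition.

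| Reading of the doubling | Share meeting it |
|---|---|
| Two samples ≤48 h apart, exact visit times | about 58% |
| Same, visit times varying by ±12 to ±24 h | 20–24% |
| Same, with a further sample 24 h later before rescue | 100% |
| Rate from the previous sample | 100% |

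The rate form requires a ratio ≥ 2^(gap in hours/48): 2.83 at 72 h and 4 at 96 h. The simulation assumes exponential growth, but a rise of at least 4-fold over any gap up to 96 h needs no such assumption. Split the gap into two halves of at most 48 h; one of them must contain at least a doubling. At 5-fold per 48 h, a 72 h gap gives 5^1.5 = 11-fold.

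**4. Size.** One reclassified participant moves a group's incidence by 100/n points: 50.0 at n=2, 33.3 at n=3, 16.7 at n=6, 5.6 at n=18. For example, if four of six truly regrow and one or two of them are rescued unconfirmed, the reported figure drops from 66.7% to 50.0% or 33.3%.

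**The case against.** Several points on the other side stand.

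- A reader might infer that everyone rescued for regrowth is scored as having none. No passage says so. The 18S sample required before rescue will often show at least 5000 parasites/mL and confirm regrowth afterwards. Only those it does not confirm are in question, and how many there will be is unknown.
- A reader might infer that sampling gaps make the criterion impossible to demonstrate. The SAP does not require two samples within 48 h, and a large rise over 72 h itself proves the doubling. Three visits a week is also a minimum, least likely to apply when counts are rising. The gap matters only under a strict pairwise reading; what is missing is a stated choice between readings.
- The PD Analysis Set (SAP 5.1.4, used in 11.1) requires a pyronaridine dose, so participants given rescue instead of pyronaridine on Day 8 are already out. The denominator point covers only early treatment after dosing.
- A reader might infer that later-cohort doses would be chosen on a biased incidence. Protocol 10.1.8 has the SDRT review parasitaemia and the available PK/PD modelling directly. The primary model uses the counts themselves and flags data after rescue (SAP 10.5).
- Errors need not all run downwards. 18S qPCR also counts non-viable parasites (Protocol 8.2.2), so a transient rise could meet the rule without true regrowth.
- With at most 18 participants, the listed parasitaemia values would let a careful reader spot a misclassified case.

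These points limit the size and reach of the concern. They do not supply the missing rule for an unconfirmed presumptive rescue.

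**Conclusion.** The point holds in a limited form. Participants rescued for presumed regrowth can be reported as having none, because the definition needs a measured threshold that rescue may prevent from being seen. Below 5000 parasites/mL in the pre-rescue sample, the status is unknown. A strict reading of the 48-hour clause can add missed cases across 72 h gaps.

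The routes identified lower a per-dose result that Protocol 9.4.3 says will be reported, by 50 points per participant at Cohort 1's two per group. The number of participants affected is not known. The growth figures rest on assumptions: a 4–6 L blood volume with drug-free growth in the first calculation, and 5- to 30-fold per 48 h in the simulation. Growth under residual drug may be slower. Regrowth incidence is a descriptive item beside the clearance endpoint, and the primary PK/PD model is not called into question. The change is worth making because it is cheap and the rule is otherwise open to more than one reading.

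Separately, Protocol 8.1.7 and 8.2.2 disagree on whether qPCR results are available in real time and must be reconciled.

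**What to change.** Amend SAP 11.1.2 and leave the clinical rescue rule as it is.

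1. **Definition.** State that the pre-rescue 18S sample is included. Confirmed regrowth is a value of at least 5000 parasites/mL after the initial reduction, with a ratio to the previous sample of at least 2^(gap in hours/48). Apply the rate form to outpatient samples. In confinement keep a literal two-fold rise between samples within 48 h, because at 4 h spacing the rate form would accept 2^(4/48) = 1.06-fold.
2. **Reporting.** Per dose group, show four categories: confirmed regrowth (C); rescue for presumed but unconfirmed regrowth (P); treated early for another reason before any regrowth (O); no regrowth through Day 47±2 (Z). Do not count O as non-events. Give incidence both ways, C/(C+P+Z) and (C+P)/(C+P+Z), with O shown beside them.
3. **Reason for rescue.** Record the reason for any early Riamet and add it to the rescue listing. Whether the eCRF already holds it cannot be seen from the documents.

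Kaplan-Meier curves per dose group are not recommended, since they say almost nothing at two participants per group. Nor should one rising value count as an event, since that would change the endpoint and could overcount.

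The cost is a few SAP sentences and at most one data field, with no extra samples. The drawback is that a few participants move to an indeterminate category, and some presumed cases might never have reached 5000 parasites/mL. That is why they are shown separately.
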